6.1.1 Lost to Follow Up

Every reasonable effort is to be made to contact any subject lost to follow-up during the course of the study to complete study-related assessments, record outstanding data, and retrieve study drug.

6.2 Discontinuation of the Site

If an investigator intends to discontinue participation in the study, the investigator must immediately inform the sponsor.

6.3 Discontinuation of the Study

The sponsor may terminate this study prematurely, either in its entirety or at any study site, for reasonable cause provided that written notice is submitted in advance of the intended termination. Advance notice is not required if the study is stopped due to safety concerns. If the sponsor terminates the study for safety reasons, the sponsor will immediately notify the investigator and subsequently provide written instructions for study termination.

7 STATISTICAL METHODOLOGY

A Statistical Analysis Plan (SAP) will be written to provide details of the analysis, along with specifications for tables, listings and figures to be produced. The SAP will be finalized before the database hard lock. Any changes from the analyses planned in SAP will be justified in the Clinical Study Report (CSR).

Prior to database lock, a Final Review of Data and TLFs Meeting will be held to allow a review of the clinical study data and to verify the data that will be used for analysis set classification. If required, consequences for the statistical analysis will be discussed and documented. A meeting to determine analysis set classifications may also be held prior to database lock.

In general, continuous data will be summarized with descriptive statistics (number of subjects, mean, standard deviation, minimum, median and maximum), and frequency and percentage for categorical data. Kaplan-Meier estimates will be provided for time-to-event endpoints. Separate data displays will be provided for the Safety Lead-in phase and phase 2 of the study unless specified otherwise.

Baseline will be defined as the last observation prior to first dose, unless otherwise specified.

7.1 Sample Size

The sample size for the Safety Lead-in phase is not based on a statistical power calculation. The planned number of up to 18 subjects would provide adequate information for the objectives of the safety cohort.

Simon's optimal 2-stage design [Simon, 1989] will be used for conducting phase 2 of the study. The null hypothesis is that the true ORR is 10%, and the alternative hypothesis is that the true ORR is 25%. The study will be carried out in 2 stages. In stage I, a total number of 13 subjects treated at the RP2D will be evaluated.

If there is 1 or fewer responses among these 13 subjects, the study will be stopped early for futility. Otherwise, an additional 21 subjects will be enrolled in stage II, resulting in a total number sample size of 34. If there are 6 or more responses among these 34 subjects, we reject the null hypothesis and claim that the treatment is promising. The design controls the type I error rate at 10% and yields the power of 80%.

7.2 Analysis Sets

Detailed criteria for analysis sets will be laid out in classification specifications and the allocation of subjects to analysis sets will be determined prior to database hard-lock.

7.2.1 Full Analysis Set (FAS)

The full analysis set (FAS) will consist of all enrolled subjects. This will be the primary analysis set for efficacy analyses.

7.2.2 Per Protocol Set (PPS)

The per protocol set (PPS) will consist of the subset of the FAS who do not meet criteria for PPS exclusion. These criteria are to capture relevant non-adherence to the protocol and will be defined in the SAP. The PPS will be a secondary analysis set for efficacy analyses. Select demographic and baseline characteristics may also be summarized for the PPS.

7.2.3 Safety Analysis Set (SAF)

The safety analysis set (SAF) consists of all subjects who took at least 1 dose of study drug, and will be used for safety analyses.

For the statistical summary of the safety data, the SAF will be used.

7.2.4 Pharmacokinetic Analysis Set (PKAS)

The pharmacokinetic analysis set (PKAS) will consist of the subset of the SAF for which at least 1 ASP1650 concentration measurement is available. Additional subjects may be excluded from the PKAS at the discretion of the pharmacokineticist. Any formal definitions for exclusion of subjects or time-points from the PKAS will be documented in the Classification Specifications and determined in the Classification Meeting. The PKAS will be used for description of pharmacokinetic data.

7.2.5 Dose Limiting Toxicity Evaluation Analysis Set (DEAS)

The dose limiting toxicity evaluation analysis set (DEAS) is defined as all subjects in SAF by excluding the subjects who meet the following criterion:

- A subject without a DLT who receives less than the planned ASP1650 dose during the DLT observation period.

DEAS will be used for the analysis of DLT data.

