2.2 Study Design and Dose Rationale

2.2.1 Study Design

This is a phase 2, open-label, single-arm, multicenter study to assess the safety and efficacy of ASP1650, an mAb targeting CLDN6, in male subjects with incurable platinum refractory germ cell tumors. Up to 46 subjects at approximately 4 centers located in the United States will participate in the study.

The study consists of 2 phases: Safety Lead-in phase and phase 2. For all subjects, the study will consist of the following periods: Screening, Enrollment, Treatment and Follow-up. Each subject may complete a maximum of 12 treatment cycles. One treatment cycle is 14 days. After discontinuation of study drug treatment, all subjects will complete a study treatment discontinuation visit and a safety Follow-up visit.

Screening and Enrollment Period

Screening will take place up to 45 days prior to enrollment. Re-screening may be allowed 1 time per subject upon discussion with the medical monitor.

Treatment Period

Safety Lead-in Phase

The Safety Lead-in phase of this study is to establish the tolerability of RP2D (ASP1650 1500 mg/m² [Q2W]). An initial dose level of ASP1650 1000 mg/m² Q2W will be evaluated in a 3-subject cohort (cohort 1), and if well tolerated, a new subject cohort (minimum 3 and up to 4 subjects) will be opened to evaluate a dose level of ASP1650 1500 mg/m² Q2W (cohort 2) according to the Bayesian Optimal Interval (BOIN) Design [Liu et al, 2015]. Based on tolerability observed in cohort 2, an additional subject cohort (cohort 3) will be opened to evaluate 1500 mg/m² Q2W (minimum 3 and up to 4 subjects) or de-escalation to 1250 mg/m² Q2W if 1500 mg/m² Q2W is not tolerable (minimum 6 and up to 8 subjects). Nine to 18 subjects will be enrolled in the Safety Lead-in phase. The RP2D determination will be based on at least 6 evaluable subjects at the RP2D as determined by the Dose Evaluation Committee (DEC).

There will be at least 3 calendar days between the treatment initiation of the first subject and treatment initiation of all subsequent subjects at the same dose level.

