The dose limiting toxicity (DLT) observation period will be from cycle 1/day 1 (C1D1) through C2D14. Evaluable subjects are defined as subjects who experience a DLT or in the absence of DLT, complete the DLT observation period. Subjects who are later discovered not to meet eligibility criteria or are not evaluable for DLT may be replaced. If no DLTs are observed in the first 6 evaluable subjects (cohorts 1 and 2), the DLT observation period for cohort 3 may be reduced to C1D1 through C1D14 (one cycle).

Dose evaluation rules based on the BOIN design with target DLT rate of 0.30 and optimal interval of (0.236, 0.359) are as follows:

Action	Number of Subjects Treated at Current Dose Level						
	3	4	5	6	7	8	9
Escalate dose if number of subjects with DLT \leq	0	0	1	1	1	1	2
Stay at current dose level if number of subjects with DLT =	1	1	-	2	2	2	3
De-escalate if number of subjects with DLT =	2*	2	2 or 3	3	3 or 4	3 or 4	4
Stop if number of subjects with DLT \geq	3	3	4	4	5	5	5

DLT: dose limiting toxicity.

*The study may be terminated instead of de-escalated upon discussion with the DEC.

The DEC will be responsible for the review of individual subject safety data in order to provide an assessment of whether reduction or escalation should occur within the next cohort and/or to determine when MTD has been reached in a given dose level. Additional details regarding responsibilities and membership requirements will be included in the DEC Charter.

Proposed Dose Levels of ASP1650

Dose Level	ASP1650	Planned Number of Subjects
1	1000 mg/m ²	3
2	1500 mg/m ²	6-8
De-escalated	1250 mg/m ²	Only if necessary based on DLTs of Dose Level 2

DLT: dose limiting toxicity

At minimum, safety data from the DLT observation period are needed for the DEC meeting, however, all available safety findings, including those occurring after the designated DLT observation period that meet DLT criteria (“delayed DLT”), will be considered.

Subjects who are tolerating study drug at a dose level concurrently under review due to DLTs in another subject, are allowed to continue dosing through week 24, as unless otherwise directed by the DEC.

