7.5 Analysis of Safety

7.5.1 Dose Limiting Toxicities

A DLT event, as defined in the DLT criteria in [Section 2.2.1 Study Design], will be summarized by cohort and dose level using DEAS. Details of DLTs will be presented in listings and subject narratives.

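### The BOIN table, the RP2D minimum and the DLT summary count subjects in three ways that do not match

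*Protocol*

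**What the plan says.** Three counts appear, and no cross-reference links them.

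- **Treated.** The columns of the BOIN decision table (Protocol synopsis and 2.2.1, SAP 2.2) are headed "Number of Subjects Treated at Current Dose Level".
- **Evaluable.** Protocol 2.2.1 and SAP 2.2 state: "Evaluable subjects are defined as subjects who experience a DLT or in the absence of DLT, complete the DLT observation period". There is no condition on dose received. The RP2D must rest on at least 6 such subjects. Replacement is optional: "Subjects who are later discovered not to meet eligibility criteria or are not evaluable for DLT may be replaced".
- **DEAS.** Protocol 7.2.5 and SAP 4.4 start from all subjects given at least one dose and exclude only "A subject without a DLT who receives less than the planned ASP1650 dose during the DLT observation period". There is no condition on completing the window. Its purpose is stated as "DEAS will be used for the analysis of DLT data", and Protocol 7.5.1 says DLT events "will be summarized by cohort and dose level using DEAS"; SAP 6.5.1 summarizes them on the DEAS by dose level.

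The DLT window runs from C1D1 to C2D14. It may be cut to one cycle for cohort 3 if the first 6 evaluable subjects have no DLT. Further detail is left to the DEC Charter (Protocol 2.2.1) and the classification specifications (Protocol 7.2, SAP 4).

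**The concern.** Establishing the RP2D through DLT assessment is a primary endpoint (Protocol 2.3.1), and cohorts are so small that one subject more or less in the denominator can move a table entry. Two things are at stake.

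- **The decision.** If one DLT-free subject is treated but does not complete the window, the column heading and the evaluable definition point to different columns. The text does not say which to read.
- **The report.** The set used to summarize DLTs is neither of these counts. The published DLT rate may therefore not be the rate on which the RP2D was accepted.

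No IDMC or DSMB is used (Protocol 10.1), so the written rule carries more weight.

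**Working it through.** **1. The plan's own table.** The inputs in Protocol 2.2.1 are a target DLT rate φ = 0.30 and the interval (0.236, 0.359). Assume the usual BOIN settings φ1 = 0.6φ = 0.18 and φ2 = 1.4φ = 0.42, which the documents do not state.

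- Lower bound: ln[(1−φ1)/(1−φ)] / ln[φ(1−φ1)/(φ1(1−φ))] = ln(0.82/0.70) / ln(0.246/0.126) = 0.2365
- Upper bound: ln[(1−φ)/(1−φ2)] / ln[φ2(1−φ)/(φ(1−φ2))] = ln(0.70/0.58) / ln(0.294/0.174) = 0.3585

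These match the stated interval. The stop row follows from a posterior probability above 0.95 that the DLT rate exceeds 0.30, under a uniform prior. Every cell for n = 3 to 9 reproduces. The table is sound; what is unclear is the count that enters it.

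**2. How one DLT-free subject is classified (two-cycle window).**

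| DLT-free subject | Treated | Evaluable | DEAS |
|---|---|---|---|
| All planned doses, observation ends after C2D1 and before C2D14 | yes | no | yes |
| Less than the planned dose, completes the window | yes | yes | no |
| Leaves before C2D1 | yes | no | no |

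If cohort 3 uses the one-cycle window, the first row applies between C1D1 and C1D14.

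**3. Effect on the table action at dose level 2 (planned 6 to 8 subjects).** Take 6 treated with 2 DLTs, where one DLT-free subject does not complete the window.

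- On treated: 2/6 = 0.333, inside the interval, so stay.
- On evaluable: 2/5 = 0.400, above 0.359, so de-escalate.

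**4. Which cells change.** Leaving out one DLT-free subject changes the action in six cells:

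| DLTs | Denominators | Actions |
|---|---|---|
| 1 | 5 vs 4 | escalate vs stay |
| 3 | 5 vs 4 | de-escalate vs stop |
| 2 | 6 vs 5 | stay vs de-escalate |
| 4 | 7 vs 6 | de-escalate vs stop |
| 2 | 9 vs 8 | escalate vs stay |
| 3 | 9 vs 8 | stay vs de-escalate |

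Nothing changes for 4 vs 3 or for 8 vs 7.

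**5. How often the 2-DLT switch could arise.** Assume 6 treated as 3+3, with 0 or 1 DLT in the first three, true DLT rate p, and each DLT-free subject uncounted independently with probability q. The documents give no value for q. No replacement is modelled.

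P(switch) = [Σ over a = 0, 1 of Bin(a; 3, p) × Bin(2−a; 3, p)] × [1 − (1−q)^4 − q^4]

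The q^4 term leaves out the case with only 2 subjects counted, which is off the table. The first bracket is 0.197, 0.259 and 0.249 at p = 0.20, 0.30 and 0.40.

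| p | q = 5% | q = 10% | q = 20% |
|---|---|---|---|
| 0.20 | 0.0365 | 0.0676 | 0.1158 |
| 0.30 | 0.0481 | 0.0892 | 0.1527 |
| 0.40 | 0.0462 | 0.0855 | 0.1465 |

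**6. Effect on the reported rate.** With 6 treated and 2 DLTs, a fully dosed subject lost after C2D1 gives 2/6 = 33.3% on the DEAS but 2/5 = 40.0% on evaluable subjects. An under-dosed subject who completes gives the reverse: 40.0% on the DEAS and 33.3% on evaluable subjects. The gap is 6.7 percentage points either way.

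**The case against.** The strongest reply has five parts.

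- **The DEAS does not drive dose decisions.** A reader might infer that it feeds the BOIN look-up. The documents do not support that. Its specified use is the DLT summary, and membership is fixed before database hard-lock. The DEC decides on individual subject data and all available safety findings. This stands: the decision conflict is treated versus evaluable only, and the DEAS is a reporting matter.
- **Context suggests that treated means evaluable.** The evaluable definition and the replacement rule come just before the table, and the RP2D minimum is in evaluable subjects. That is a natural reading, but neither document states it. The minimum prevents an RP2D from being declared on 5 evaluable subjects; it does not say which column to read when 5 are evaluable and 6 were treated.
- **The discordant subjects are uncommon.** An infusion reaction that permanently ends the infusion is itself a DLT, and after a grade 2 reaction the infusion is resumed (Protocol 5.1.2.3). Adverse events are collected to 30 days after the last dose unless new anticancer treatment starts, so stopping treatment alone does not end observation. This limits the frequency. Reduced second doses, withdrawal, loss to follow-up and new therapy remain.
- **Some flips have no effect.** Escalate and stay are equivalent at 1500 mg/m², where no higher level is planned, and dose level 1 is planned at 3 subjects. So 1 DLT in 4 versus 5 does not matter at the planned sizes.
- **Detail may sit in the DEC Charter or the classification specifications.** It may, but the public text defers to them without resolving the count, and the SAP repeats all three definitions.

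**Conclusion.** The concern holds as a conflict between stated rules for a primary endpoint. On the literal text, 2 DLTs with 6 treated and 5 evaluable gives two different table actions. The DLT rate reported on the DEAS can differ from the evaluable rate in either direction, by 6.7 percentage points in the six-subject example.

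The size is modest and conditional. The switch has probability about 4% to 15% over assumed uncounted rates of 5% to 20% and true DLT rates of 0.20 to 0.40, with no replacement. These figures are illustrations.

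Two stronger readings are not supported. A reader might infer that any reclassified subject changes the action, but only the listed cells do. A reader might also infer that early leavers in general are counted as DLT-free. Under the two-cycle window the DEAS already excludes DLT-free subjects who leave before C2D1, so the downward bias is limited to fully dosed subjects lost between C2D1 and C2D14.

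This should be corrected but does not undermine the design. No view is taken on which dose action is right.

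**What to change.** Reconcile the passages to one stated DLT-evaluable set.

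- Add the completion condition to the DEAS (Protocol synopsis and 7.2.5, SAP 4.4), so that a DLT-free subject without a complete observation period is not counted as DLT-free.
- State in one place whether a planned-dose condition also applies. The documents do not settle this, and no choice is proposed here.
- Label the BOIN columns with that same count (Protocol synopsis and 2.2.1, SAP 2.2), and use it for the six-subject minimum.
- Report DLTs on the count the DEC used. If decisions have already been taken, say which count that was.

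With one count, each dataset maps to one table action. The cost is wording in both documents; the protocol already allows non-evaluable subjects to be replaced.

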7.3 Demographics and Baseline Characteristics

Demographics and baseline characteristics will be summarized by cohort and dose level and overall for FAS and SAF.

7.3.1 Subject Disposition

The number and percentage of subjects who completed and discontinued treatment and reasons for treatment discontinuation will be presented for all FAS subjects and for subjects in the SAF by cohort, dose level and overall. Similar tables for screening disposition and follow-up disposition will also be presented. All disposition details and dates of first and last evaluations for each subject will be listed.

7.3.2 Previous and Concomitant Medications

All previous and concomitant medications will be presented in a listing. The frequency of concomitant medications (prescription, over-the-counter and nutritional supplements) will be summarized by cohort and dose level.

7.3.3 Medical History

Medical history for each subject will be presented in a listing.

7.4 Analysis of Efficacy

Efficacy analysis will be conducted on the FAS and PPS. The interpretation of results from statistical tests will be based on the FAS. The PPS will be used to assess the robustness of the results from the statistical tests based on the FAS. Response assessment will be based on modified RECIST v1.1, RECIST v1.1 alone and serum marker alone.

7.4.1 Analysis of Primary Endpoint

7.4.1.1 Objective Response Rate

ORR is defined as the proportion of subjects for each dose level whose best overall response is rated as confirmed CR or PR by modified RECIST v1.1. ORR by dose level will be calculated and its 90% confidence interval will be constructed by Clopper-Pearson method.

7.4.1.2 Sensitivity Analysis

ORR, as assessed by RECIST v1.1, by dose level will be calculated and its 90% confidence interval will be constructed by Clopper-Pearson method.

7.4.1.3 Subgroup Analysis

The following subgroups may be explored:

- Seminoma vs nonseminoma
- Prior lines of therapy: 2 vs ≥ 3
- Primary testicular site vs other (mediastinal or retroperitoneum)
- Presence of visceral metastases: yes vs no
- Late relapse: yes vs no
- Prior high-dose chemotherapy: yes vs no

7.4.2 Analysis of Secondary Endpoints

7.4.2.1 Clinical Benefit Rate

CBR is defined as the proportion of subjects for each dose level whose best overall response is rated as confirmed CR, PR or durable SD. Durable SD is a SD maintained for at least 12 weeks. CBR by dose level will be calculated and its 90% confidence interval will be constructed.

7.4.2.2 Duration of Response

DOR will be calculated only for the subgroup with confirmed response CR/PR. The distribution of DOR will be summarized only for subjects receiving the phase 2 dose level using Kaplan-Meier methodology.

7.4.2.3 Progression-free Survival

PFS is defined as the time from the date of first dose until the date of disease progression, or until death due to any cause. If a subject has neither progressed nor died, the subject will be censored at the date of last disease assessment. More detailed censoring algorithm will be provided in the SAP.

The distribution of PFS will be summarized only for subjects receiving the phase 2 dose level using Kaplan-Meier methodology.

7.5 Analysis of Safety

7.5.1 Dose Limiting Toxicities

A DLT event, as defined in the DLT criteria in [Section 2.2.1 Study Design], will be summarized by cohort and dose level using DEAS. Details of DLTs will be presented in listings and subject narratives.

7.5.2 Adverse Events

AEs will be coded using the MedDRA.

TEAE is defined as an AE observed after starting administration of the study drug and up to 30 days after the last dose of study drug.

The number and percentage of subjects with treatment-emergent AEs, SAEs, AEs leading to withdrawal of treatment, and AEs related to study drug will be summarized by System Organ

Class, preferred term, cohort and dose level. The number and percentage of AEs by severity will also be summarized. All AEs will be listed.

A study drug-related TEAE is defined as any TEAE with a causal relationship of YES by the investigator.

7.5.3 Laboratory Assessments

For quantitative laboratory measurements, descriptive statistics will be used to summarize results and change from baseline for subjects in the SAF by cohort, dose level and time point. Shifts from baseline to the worst grade based on NCI-CTCAE during treatment period in laboratory tests will also be tabulated.

Laboratory data will be displayed in listings.

7.5.4 Vital Signs

Descriptive statistics will be used to summarize vital sign results and changes from baseline for subjects in the SAF by cohort, dose level and time point.

Potentially clinically significant vital signs will be defined and tabulated as described in the SAP. Vital signs data will be displayed in listings.

7.5.5 Routine 12-lead Electrocardiograms

The 12-lead ECG results will be summarized by cohort, dose level and time point. A shift analysis table showing shifts from baseline in overall ECG (normal and abnormal) will be provided.

7.5.6 Eastern Cooperative Oncology Group Performance Status

Summary statistics (number and percent of subjects) for each category of the ECOG performance status at each assessment will be provided. The change from baseline to final visit or early termination will also be summarized. Negative change scores indicate an improvement. Positive scores indicate a decline in performance.

7.6 Analysis of Pharmacokinetics

Descriptive statistics will include the number of subjects (n), mean, standard deviation, coefficient of variation (CV), geometric mean, geometric CV, median, minimum, maximum.

7.6.1 Serum Concentrations

Serum concentrations of ASP1650 will be listed and summarized using descriptive statistics by dose and scheduled time point. Standard graphics including mean serum concentration-time profiles, overlay (spaghetti) plots will be produced.

